### **6.6.4 TMDS staff participating in questionnaire/focus group**

A waiver of documentation of consent to participate will be obtained in English from MotoMeds staff members. The rational is that staff focus groups are likely to be performed over Zoom or a similar video-conferencing software.

[figure not shown]
**6.7 Workflow.** The call center will operate during the nighttime (exact hours will be determined from INACT1-G). Staffing will be elastic to the needs of the call center case volume. If there are multiple calls at one time, the call center will be staffed to field 1-2 calls at a time. If the call volume is greater than expected, the calls will be placed on hold until a call center EMT is available. If the delivery/household visit volume is greater than the capacity to respond, the contingency plan is as follows: A restriction ('cap') will be activated such that no more than 3 participants can be waiting for a delivery at one time. If there are more than 3 participants waiting, the participants will receive advice by phone and will not receive a delivery/household visit. These cases will be recorded as study data. If volume consistently exceeds the planned capacity, the number of staff (EMTs and drivers) will be increased as funding allows.

Call intake will be managed by the HIPAA-compliant call center software Twilio and case dispatch will be managed by the Beacon Crisis Response. Dispatch alerts via Beacon will include the caller's name, phone number, location, as well as patient complaints; Beacon is also HIPAA-compliant.

Severe cases, certain fever cases and cases with unsuccessful deliveries will be contacted by phone within 24 hours (maximum of 2 attempts over the course of another 24 hours) and all participants will be contacted (maximum of 3 attempts) at 8-12 days to ascertain disposition, if additional care was sought, and qualitative feedback about the service. Responses will be recorded on paper forms and/or directly into REDCap.

Focus groups with TMDS staff will be performed to determine service usability and acceptability from an operational perspective.

**6.8 Clinical procedures.** The clinical guidelines will adhere to Ghanaian and WHO standards of care and have been developed in collaboration with Ghanaian and US government experts in malaria. During each call it will be disclosed that the call center objectives are to provide pre-emergency health support and conduct research to improve nighttime access to standard of care. To identify emergency cases, triage will occur at the level of the call center EMT (mild, moderate, and severe, see clinical guideline appendix) and leverage WHO derived danger signs for life-threatening illness. If the EMT identifies a

**Figure 3. MotoMeds Workflow.** Follow-up calls will be placed within a range of 8-12 days.

danger sign at the call center or household and thus triages the case as severe, the EMT will advise the patient to seek care at a medical facility and will offer to refer the patient to NAS emergency dispatch (for an ambulance to be dispatched if so desired by the caller).

The clinical guidelines define the clinical scope of the TMDS (also discussed above in the inclusion criteria section). This study is being conducted in an area with high pediatric morbidity and mortality from malaria. Our approach is to follow WHO standards of 'test and treat'. Febrile patients will all be tested with a commercial RDT for malaria. RDT positive patients will be treated with antimalarials. Caregivers of RDT negative patients who do not have another source of their fever will receive a next-day follow-up phone call.

A follow-up call will be placed within 24 hours for severe cases and for those mild/moderate cases with a fever without source and a negative RDT as described above. If a case is triaged as mild or moderate (no danger signs identified), local EMTs will conduct a phone-based assessment. If the patient household is outside the delivery zone, consult alone will be provided as a clinical case; the data from these encounters will not be recorded as study data, given that these patients represent a different patient population. Therefore, they will not receive a waiver of informed consent or follow-up call. If the household is inside the delivery zone (Jamestown/Usshertown), the EMT will generate a treatment plan and medications/fluids will be delivered to the household. A follow-up call will be placed at 8-12 days, ideally at 10 days. In the INACT2-G pilot study, all patient participants will receive a paired in-person exam at a household visit.

The clinical approach will be standardized across EMTs at the call center and at the household. Standardization will occur through paper and/or digital guideline generation for the common chief complaints identified in INACT1-G. Each call center assessment will produce a treatment plan that may include direction to seek emergency care, clinic follow-up, fluids, and/or basic medications (see clinical guideline appendix). The clinical guidelines and workflow (Figure 3) were localized to standards of practice (e.g. selection of guideline-recommended antimalarial medications) and epidemiology (high malaria burden).

Neither the ability to receive care nor the type of care will be affected by the decision to participate in the study. If a family declines to consent to inclusion in the research study, evaluation/care will be provided as outlined in the clinical guidelines. The data from this encounter will not be recorded as study data.

All household medication/fluid deliveries will be accompanied by an EMT with the intent that the medication handoff will happen after the EMT examines the patient and any necessary adjustments to the treatment plan are made. If patients are excluded from participation in the study, standard of care information will be conveyed and/or indications for seeking emergency care. The data from this interaction will not be recorded as study data.

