## **6.10 Outcome Measures.**

**6.10.1 Aim I (clinical safety).** Establish rate of guideline adherence at the call center (primary outcome measure) and household. Determine sensitivity and specificity of each clinical variable using the in-person exam at the household as the reference standard. Establish congruence between call center and in-person assessment in terms of severity categorization, danger signs, disease type, and treatment. Determine clinical status at 8-12 days. Since evaluation of guideline adherence and congruence between the call center and household are part of the research question itself, and because clinical equipoise can exist beyond what can be reflected in written guidelines, small deviations from guidelines based on the clinical facts of the case are not considered protocol violations. Violations that led to an adverse or severe adverse effect will be reported as further specified in this study protocol.

**6.10.2 Aim II (feasibility from patient perspective).** Logistical data on patient workflow will be collected (duration of call, time to delivery). Parent/guardian feedback will be collected on the clinical, cost and quality aspects of the TMDS.

**6.10.3 Aim III (feasibility from staff perspective).** Domains of inquiry are clinical decision making, formulation of medications, communication with team members and households, and unanticipated opportunities for improvement.

**6.11 Data collection.** During the initial call, study staff will capture household contact information, details of the illness assessment and treatment recommendations from all callers meeting inclusion criteria. During the home visit the EMT will capture details of the in-person illness assessment and physical exam that includes anthropometric measurements (MUAC), vital signs, and/or RDT results. During the follow-up call, study staff will capture information on illness progression, outcome, and service feedback. During staff focus groups, a third party will capture staff opinions relating to service operations.

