**6.13 Staffing and Training.** The TMDS will be staffed by Ghanaian medical professionals including physicians and Advanced EMTs. On-call physicians with experience in pediatrics will provide supervision of guidelines and care. Consults will be flexible to mode of communication as to local standards of care; this may involve modes of communication beyond voice (e.g. images, video). If these modes are used, they will always occur with direct end-to-end encryption and they will not be saved nor used as research data. This flexibility prioritizes safety and yet respects protected health information. The staff will be trained on this distinction. All EMTs will have completed a minimum of 2 years of medical education at the NAS Paramedic and Emergency Care Training School or an equivalent institution. They will receive incoming calls, conduct phone assessments following standard of care guidelines, and make treatment recommendations. They will also perform consent and in-person assessments during home visits and will complete follow-up calls. Advanced EMTs will not make independent decisions but rather act within the scope of pre-defined clinical guidelines and/or consult on-call physicians. Trained local motorcycle taxi drivers will be contracted to deliver any needed medications, drive study EMTs to and from home visits. All staff members will be trained in occupational safety measures and human research protections. Staff members will receive training specific to this study, the clinical guidelines and study procedures by the PI and CIs and will undergo an assessment by the PI/CIs prior to being cleared for participation at the TMDS. They will receive on-going supervision by the PI/CIs and a NAS paramedic supervisor who completed paramedic-level training in the United States.

**6.14 Incentives.** No monetary benefits will be offered for participation in this study.

**6.15 Costs.** There is no cost for families to participate in this study and/or receive care.

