### **6.18 Data Analysis**

Data will be aggregated with REDCap and analyzed in R. Statistical support will be provided by the UF Clinical and Translational Science Institute.

Quantitative data will be analyzed using frequentist statistics, which will include using proportions for categorical variables, median and interquartile ranges for quantitative variables, effect size, sensitivity/specificity calculations, interrater agreement (e.g. Cohen's kappa). Qualitative data will be transcribed, coded to evaluate themes, and summarized to identify opportunities for improvement.

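### The household reference exam is not protected from knowledge of the call-center assessment, so agreement on history items, severity, disease type and especially treatment is liable to be inflated by an unknown amount

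*Combined protocol and SAP*

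**What the plan says.** Section 6.10.1 sets two tasks that depend on the household exam. The first is "Determine sensitivity and specificity of each clinical variable using the in-person exam at the household as the reference standard". The second is "Establish congruence between call center and in-person assessment in terms of severity categorization, danger signs, disease type, and treatment". Section 6.18 lists "sensitivity/specificity calculations, interrater agreement" among the statistics, with Cohen's kappa as the example. Section 5 places congruence among the primary objectives of Aim I, although the primary outcome measure is guideline adherence at the call center.

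On how the visit runs:

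- Section 6.8: "Each call center assessment will produce a treatment plan". An EMT travels with every delivery, and "the medication handoff will happen after the EMT examines the patient and any necessary adjustments to the treatment plan are made".
- Section 6.7: the dispatch alert gives the caller's name, phone number, "location, as well as patient complaints".
- Section 6.9: a child counts as febrile if the parent reported fever at the call center or at the household, or if fever is measured at the visit. Febrile children are tested at the household.
- Section 6.13: the EMTs take calls and make the phone assessments. "They will also perform consent and in-person assessments during home visits". Section 6.5.3 expects 5 to 15 call-center EMTs.
- Section 6.11: the household EMT records the illness assessment and physical exam. The order relative to seeing the call-center record is not given.

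The limitations in section 6.19 do not mention the independence of the two assessments.

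**The concern.** A reference standard should be read without knowledge of the result that it checks. Here the household EMT holds the medications chosen by phone, has the complaints, and edits an existing plan. Where the EMT is unsure, the call finding is available as a default. A phone error that is repeated at the household is then counted as agreement.

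What is at stake is the paired comparison. Section 6.19 describes the study as designed to compare phone and in-person assessment, and section 8 relies on monitoring that concordance to control the risk of understated severity. If the reference leans toward the phone result, some phone errors will not show up. The order of recording cannot be reconstructed after enrollment, so it has to be set in advance.

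**Working it through.** **The plan's own figure.** The only computed precision is for call-center adherence (section 6.12): 1.96 × √(0.86 × 0.14 / 819) = 0.0238, which reproduces the stated ±2.4%. It does not use the household exam as reference, so this point does not change it. No precision is given for sensitivity, specificity or kappa.

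**What the household EMT knows.**

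| Item | Support in the text |
|---|---|
| Treatment plan and medications | Clear implication of 6.8 |
| Complaints | Stated in 6.7 |
| Fever reported at the call | Needed to apply the testing rule in 6.9 |
| Call-center severity, danger-sign answers, disease type | Not listed in the alert; inferred only |

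**Direction.** Let TP, FP, FN and TN be the shares of pairs, phone against an independent household exam. Let q be the share of discordant pairs in which the household record takes over the phone finding. Then

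- TP′ = TP + q·FP, FP′ = (1 − q)·FP
- FN′ = (1 − q)·FN, TN′ = TN + q·FN

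Sensitivity TP′/(TP′ + FN′) rises because TP grows and FN shrinks. Specificity rises in the same way. For kappa the direction was checked numerically: in 99,727 random tables with better-than-chance accuracy, with q allowed to differ for positive and negative calls, carry-over lowered none of the three statistics.

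**Size, illustration only.** The documents give no prevalence, no blinded accuracy and no q. All inputs here are assumptions.

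Worked case: prevalence 0.30, sensitivity 0.70, specificity 0.80, so TP = 0.21, FN = 0.09, FP = 0.14, TN = 0.56. With q = 0.10:

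- TP′ = 0.224, FP′ = 0.126, FN′ = 0.081, TN′ = 0.569
- sensitivity = 0.224/0.305 = 0.73; specificity = 0.569/0.695 = 0.82
- observed agreement = 0.793; chance agreement = 0.35 × 0.305 + 0.65 × 0.695 = 0.5585
- kappa = (0.793 − 0.5585)/(1 − 0.5585) = 0.53

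| Assumed prevalence / sensitivity / specificity | q | Sensitivity | Specificity | Kappa |
|---|---|---|---|---|
| 0.30 / 0.70 / 0.80 | 0 | 0.70 | 0.80 | 0.48 |
| | 0.10 | 0.73 | 0.82 | 0.53 |
| | 0.25 | 0.78 | 0.85 | 0.61 |
| | 0.50 | 0.86 | 0.90 | 0.74 |
| 0.10 / 0.60 / 0.90 | 0 | 0.60 | 0.90 | 0.41 |
| | 0.10 | 0.66 | 0.91 | 0.48 |
| | 0.25 | 0.73 | 0.92 | 0.57 |
| 0.05 / 0.50 / 0.95 | 0 | 0.50 | 0.95 | 0.37 |
| | 0.10 | 0.57 | 0.96 | 0.44 |
| | 0.25 | 0.66 | 0.96 | 0.55 |

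**An opposing effect.** The child may change between call and visit (the delivery benchmark in section 5 is under 2 hours). In the first scenario, let the household status flip at random in 10% of pairs. TP becomes 0.21 × 0.9 + 0.14 × 0.1 = 0.203; likewise FP = 0.147, FN = 0.137 and TN = 0.513. With q = 0.10 the results are sensitivity 0.64, specificity 0.80 and kappa 0.43, at or below the independent 0.70 / 0.80 / 0.48. With q = 0.25 they are 0.70 / 0.83 / 0.53. The net direction therefore depends on two unknowns.

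**Danger signs.** Section 6.6.3 names danger signs as a reason for no visit, and section 6.19 says that no in-person data will be obtained on emergent patients. If that holds, visited children are all phone-negative, so TP = FP = 0. With any sign found at the household, sensitivity is 0, specificity is 1 and kappa is 0, whatever q is. The model above does not describe this item.

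**The case against.** The strongest reply is that the documents show an opportunity for anchoring and no bias that has occurred. That stands. A reader might infer that the statistics are in fact inflated, and inflated across the board. The text does not support this: q is unknown and could be zero, and real change in the child works against it. MUAC, measured vital signs and RDT results leave less room to repeat a phone finding. Danger-sign sensitivity and kappa are limited by the separate problem of missing pairs.

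A reader might also infer that the call taker usually makes the visit. The wording points the other way. Section 6.8 speaks of EMTs at the call center and at the household. Section 6.7 has callers wait for a call-center EMT and sends dispatch details that a call taker would already have. Interrater agreement presupposes two raters. Two EMTs per case is the more natural reading, but no rule requires it, and a second EMT who knows the plan is still not masked.

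Two further objections stand in part. Figure 3, the clinical guideline appendix and the data collection instruments are not in the text available for review, so a masking step there cannot be excluded. And no form order can hide medications that the EMT is carrying, so the remedy is only partial. Neither removes the case for stating the recording order in the protocol.

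**Conclusion.** The point holds as a risk to the secondary Aim I measures. The reference exam is made with knowledge of the call-center plan and complaints, and no text available for review separates the two assessments. Sensitivity, specificity and kappa for non-emergent history items, the mild/moderate category and disease type are liable to be inflated. Treatment congruence is most exposed, because the household plan is by design an edit of the phone plan.

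The amount cannot be estimated from the design. The illustrated rises in kappa (0.05 to 0.07 at 10% carry-over, 0.13 to 0.18 at 25%) rest wholly on assumed prevalence, accuracy and carry-over, and on no change in the child between call and visit. They are not estimates for this study. It would be wrong to read this as a challenge to the primary outcome: call-center guideline adherence and its ±2.4% stand. The change is worth making because it is cheap and cannot be made retrospectively.

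**What to change.** 1. In sections 6.8 and 6.11, state that the household EMT records findings, severity, disease type and intended treatment, with a time stamp, before opening the call-center form. The two records are then reconciled before medication handoff, with both entries kept and the first one used for congruence. Call-reported fever stays available for the testing rule in 6.9.
2. Record the IDs of the call-center EMT and the household EMT for every pair. Use a different EMT from the call taker where existing staffing allows.
3. In section 6.18, report congruence with and without same-EMT pairs.
4. In section 6.19, state that carried medications and dispatched complaints leave residual anchoring, above all for treatment congruence.
5. If the instruments or Figure 3 already contain such a step, say so in 6.8 and 6.11; that would settle the recording-order part.

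The cost is a changed form order at the household, one time stamp and two ID fields. No extra staff or procedures are needed, and all call information is still to hand before treatment is final. The drawback is that masking remains partial.

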## **6.9 Testing.**

**Malaria:** Rapid diagnostic tests will be used to evaluate malaria as a source of fever in all febrile patients; febrile is defined as parent/guardian report of fever at the call center or household or objectively measured fever at the household visit. EMTs trained in rapid

diagnostic testing will perform the test at the household. A positive malarial RDT will be used to initiate anti-malarial treatment. A finger prick will be performed with a retractable safety lancet, up to 0.5 ml of blood will be collected in a capillary/collection tube and spotted onto the RDT.

## **6.10 Outcome Measures.**

**6.10.1 Aim I (clinical safety).** Establish rate of guideline adherence at the call center (primary outcome measure) and household. Determine sensitivity and specificity of each clinical variable using the in-person exam at the household as the reference standard. Establish congruence between call center and in-person assessment in terms of severity categorization, danger signs, disease type, and treatment. Determine clinical status at 8-12 days. Since evaluation of guideline adherence and congruence between the call center and household are part of the research question itself, and because clinical equipoise can exist beyond what can be reflected in written guidelines, small deviations from guidelines based on the clinical facts of the case are not considered protocol violations. Violations that led to an adverse or severe adverse effect will be reported as further specified in this study protocol.

**6.10.2 Aim II (feasibility from patient perspective).** Logistical data on patient workflow will be collected (duration of call, time to delivery). Parent/guardian feedback will be collected on the clinical, cost and quality aspects of the TMDS.

**6.10.3 Aim III (feasibility from staff perspective).** Domains of inquiry are clinical decision making, formulation of medications, communication with team members and households, and unanticipated opportunities for improvement.

**6.11 Data collection.** During the initial call, study staff will capture household contact information, details of the illness assessment and treatment recommendations from all callers meeting inclusion criteria. During the home visit the EMT will capture details of the in-person illness assessment and physical exam that includes anthropometric measurements (MUAC), vital signs, and/or RDT results. During the follow-up call, study staff will capture information on illness progression, outcome, and service feedback. During staff focus groups, a third party will capture staff opinions relating to service operations.

Data collection instruments will include paper screening forms and paper case report forms, digital data collection forms (e.g. REDCap; see data collection instruments) and zoom recordings. Data collected on participants that refuse consent (e.g. initial call center data) will be kept to enumerate rates of study exclusion and reasons for refusal of consent; the data will be excluded from analysis and will be maintained confidentially. Data may be collected up to 12 days after the initial call. Participants may be contacted by phone for clarifications up to 365 days after the initial call. Paper documents will only be accessed by trained clinical and study personnel and will be secured in a locked cabinet in Ghana. These documents will be scanned and uploaded onto a UF secure server.

**6.12 Sample size calculation.** The enrollment is based on TMDS census over the study period which is estimated to be 819 patient participants. Determination of the effect size of guideline adherence at the call center is the primary outcome. If the call center treatment

plan adheres to the clinical guidelines for 86% of cases (data from INACT2-H), then a sample size of 819 (1.5 patients per night) will estimate guideline adherence to within a 95% confidence interval of +/- 2.4%.

**6.13 Staffing and Training.** The TMDS will be staffed by Ghanaian medical professionals including physicians and Advanced EMTs. On-call physicians with experience in pediatrics will provide supervision of guidelines and care. Consults will be flexible to mode of communication as to local standards of care; this may involve modes of communication beyond voice (e.g. images, video). If these modes are used, they will always occur with direct end-to-end encryption and they will not be saved nor used as research data. This flexibility prioritizes safety and yet respects protected health information. The staff will be trained on this distinction. All EMTs will have completed a minimum of 2 years of medical education at the NAS Paramedic and Emergency Care Training School or an equivalent institution. They will receive incoming calls, conduct phone assessments following standard of care guidelines, and make treatment recommendations. They will also perform consent and in-person assessments during home visits and will complete follow-up calls. Advanced EMTs will not make independent decisions but rather act within the scope of pre-defined clinical guidelines and/or consult on-call physicians. Trained local motorcycle taxi drivers will be contracted to deliver any needed medications, drive study EMTs to and from home visits. All staff members will be trained in occupational safety measures and human research protections. Staff members will receive training specific to this study, the clinical guidelines and study procedures by the PI and CIs and will undergo an assessment by the PI/CIs prior to being cleared for participation at the TMDS. They will receive on-going supervision by the PI/CIs and a NAS paramedic supervisor who completed paramedic-level training in the United States.

**6.14 Incentives.** No monetary benefits will be offered for participation in this study.

**6.15 Costs.** There is no cost for families to participate in this study and/or receive care.

**6.16 Study endpoint and timeline** Advertisement of the call center and outreach will begin in the month prior to starting the service. Enrollment will take place over 9 months (estimated November 2022 to July 2023). If the minimum enrollment of 819 patients is reached before 9 months, enrollment will continue for the full 9 months to assess sustainability. No more than 2000 patients will be screened/enrolled without subsequent IRB approval. If the minimum enrollment is not reached by 9 months, the enrollment period will be extended to a maximum of 15 months. IRB approval will be requested for further extension beyond 15 months. Primary analysis may continue up to 5 years after study conclusion. See data collection section for duration of enrollment per participant.

**6.17 Data Security** Paper-based survey forms will be handled by staff trained in the protections of personal health information; forms will be stored in a locked cabinet in Ghana. Data collected electronically will use a HIPAA compliant survey tool (e.g. REDCap and server). All devices will be password protected and encrypted. The de-identification plan for data publication is as follows: Names and phone numbers will be removed. Each case will be given a de-identified number that will be used to link the data sources. Upon publication, these ID numbers will be removed and replaced with a random generated

number and there will be no key to link the files. De-identified data will be shared with the USAID.

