### **6.6.3 Parent/guardian participants not receiving a household visit**

For parent/guardian participants that are not receiving a household visit due to danger signs present, met capacity, or failed/declined delivery, a waiver of documentation of consent will be presented at the time of the initial call or at the time of the follow-up call (either 24-hour or at the 8-12-day follow-up call). The rationale for the waiver of documentation of consent is that the survey questions pose no more than minimal risk and written consent is not logistically feasible. Explanation of informed consent procedures may be obtained in English (official language of Ghana) or another locally spoken language (ex: Ga) in which the EMT obtaining consent and the participant providing consent are fluent as is common research practice in Ghana (see Gamada Letter of Support).

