### **6.19 Limitations**

*Low sample size.* Household visits at nighttime are logistically challenging, therefore the study area must be limited in size to ensure safety and efficiency. The size of the study area dictates the population eligible for enrollment. Prior to commencing the intervention, it is difficult to assess whether the designated study area will provide adequate call volume to reach enrollment. We will address this limitation through active advertisement.

*Enrollment biases.* The intervention is intended to provide pre-emergency care to children who are experiencing a health problem during nighttime hours. Due to the lack of affordable, qualified healthcare options in the study area, households who could potentially visit a health center during the day may wait until nighttime to take advantage of the call center service. This could bias our understanding of the nighttime healthcare needs and call center functionality.

*Geographic bias.* The call center will be advertised as a service for households in a specific geographic area. In Ghana, boundaries at the community level (US equivalent to neighborhoods) are not officially defined and the address system is based on proximity to landmarks. As a result, it is possible that some callers outside of the study area could be enrolled or some callers inside the study area could be excluded, although the former is more likely to occur. While a 'fuzzy radius' impacts logistics, we do not anticipate this to impact the primary outcomes.

*Limited scope.* The study is designed to evaluate congruence of phone vs in-person assessments for non-emergent patients. Emergent patients will be advised to seek care immediately. The exclusion of emergency patients limits the scope and generalizability of the study to the full spectrum of EMS services. In-person data on emergent patients will not be obtained in this study.

*Limited diagnostic ability.* The study is designed to provide acute care at the community level; thus, it is not possible for gold standard diagnostics such as microscopy and PCR to directly inform individual treatment plans. For malaria, in lieu of microscopy, point-of-care rapid diagnostic testing may be used for diagnosis.

---

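### Danger-sign sensitivity and specificity against the household exam cannot be estimated, because a danger sign on the phone removes that exam; missed signs can be counted, but over-triage cannot be checked in person

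*Combined protocol and SAP*

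**What the plan says.** Section 6.10.1 (Aim I, clinical safety) states two analyses that use the household exam:

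- Accuracy: "Determine sensitivity and specificity of each clinical variable using the in-person exam at the household as the reference standard".
- Agreement: "Establish congruence between call center and in-person assessment in terms of severity categorization, danger signs, disease type, and treatment".

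Section 6.18 names sensitivity and specificity calculations and gives Cohen's kappa as an example of an agreement statistic. It mentions no method for cases without the reference exam.

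The workflow decides who gets that exam:

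- Section 6.8: a danger sign makes the case severe, and the family is advised to go to a facility. The delivery pathway is for the rest: "If a case is triaged as mild or moderate (no danger signs identified), local EMTs will conduct a phone-based assessment".
- Section 6.6.3 describes callers "not receiving a household visit due to danger signs present, met capacity, or failed/declined delivery".
- Section 6.7, on the delivery cap: "If there are more than 3 participants waiting, the participants will receive advice by phone and will not receive a delivery/household visit".
- Section 6.19: "The study is designed to evaluate congruence of phone vs in-person assessments for non-emergent patients", and "In-person data on emergent patients will not be obtained in this study".

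Section 6.8 also says the opposite: "In the INACT2-G pilot study, all patient participants will receive a paired in-person exam at a household visit".

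**The concern.** Sensitivity needs children who are positive on both the phone and the exam. Specificity needs children who are positive on the phone and negative on the exam. For danger signs the workflow supplies neither, because a positive phone result removes the exam. An analyst who follows 6.10.1 and 6.18 literally would report figures set by the workflow under a clinical-safety objective.

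The two triage errors are affected differently. Under-triage (no sign on the phone, a sign at the household) can be seen in visited children, so the concordance monitoring promised in section 8 can detect it. Over-triage cannot be checked in person. Section 8 lists the cost of an unnecessary referral as a risk and expects it to touch a small share of families. The paired data cannot test that expectation.

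**Working it through.** **The plan's only precision figure.** Section 6.12 gives a half-width of 2.4 points for 86% guideline adherence with 819 patients. It reproduces: 1.96 × √(0.86 × 0.14 / 819) = 2.38 points. It concerns the primary outcome. No precision is stated for sensitivity or specificity.

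**Which cells are observed.** Cross phone danger sign (yes/no) with household danger sign (yes/no):

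| | Household yes | Household no |
|---|---|---|
| Phone yes | TP, not examined | FP, not examined |
| Phone no | FN, seen if visited | TN, seen if visited |

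Using visited children only:

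- sensitivity = TP/(TP + FN) = 0/(0 + FN) = 0%, or 0/0 if nothing is missed;
- specificity = TN/(TN + FP) = TN/(TN + 0) = 100%;
- kappa: every phone result is negative, so observed and chance agreement both equal TN/(FN + TN), and kappa is 0 (undefined if FN = 0).

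No rate enters these results. A severe/non-severe kappa fails in the same way.

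**Illustration.** The documents give no danger-sign prevalence or phone accuracy, so these inputs are assumptions: 819 calls, 10% prevalence (82 children), true sensitivity 90%, true specificity 95%, and every phone-non-severe child visited.

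- TP = 74, FN = 8, FP = 37, TN = 700.
- Phone-severe and unexamined: 74 + 37 = 111. Visited: 8 + 700 = 708.
- Raw agreement = 700/708 = 98.9%; chance agreement = 700/708; kappa = 0.
- Under-triage = 8/708 = 1.1% (exact 95% CI 0.5 to 2.2%).

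With true sensitivity 50%, FN = 41 and under-triage = 41/741 = 5.5% (4.0 to 7.4%). The under-triage rate responds to phone performance; the naive sensitivity stays at 0%.

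**Range of assumptions.** Prevalence 5, 10 or 15%, sensitivity 90, 70 or 50%, specificity 95%, and 100% or 80% of phone-non-severe children visited make 18 combinations. All return 0%, 100% and kappa 0. Raw agreement runs from 91.5% to 99.5%, and under-triage from about 0.5% to 8.5%.

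**What the data leave open.** Hold the observable data fixed at 111 phone-severe, 8 missed and 700 confirmed negative, and vary the unseen number of true positives:

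| TP among the 111 | Sensitivity | Specificity | Over-triaged |
|---|---|---|---|
| 0 | 0/8 = 0% | 700/811 = 86.3% | 111 |
| 28 | 28/36 = 77.8% | 700/783 = 89.4% | 83 |
| 74 | 74/82 = 90.2% | 700/737 = 95.0% | 37 |
| 111 | 111/119 = 93.3% | 700/700 = 100% | 0 |

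All four rows give the same study data.

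**Under-triage does not stand in for over-triage.** At 10% prevalence and 90% sensitivity, lowering specificity from 99% to 85% raises over-triaged calls from 7 (7/819 = 0.9%) to 111 (111/819 = 13.6%). Under-triage moves only from 8/738 = 1.1% to 8/634 = 1.3%.

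**The case against.** The strongest reply is that the plan never says in terms that danger signs will have a sensitivity and specificity. Section 6.10.1 does not define its clinical variables and names danger signs only under congruence; the guideline appendix and data forms, which might settle this, are not in the available text. Section 6.19 already confines the phone versus in-person comparison to non-emergent patients. Kappa is only an example, and raw agreement can still be computed.

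Part of this stands. The term is undefined, and severity category in particular is named only under congruence. But a plan that covers every clinical variable naturally includes danger signs, and the kappa problem arises from the congruence sentence on either reading. Section 6.19 presents the restriction as a limit on scope and generalizability; it does not withdraw or redefine the estimates in 6.10.1 and 6.18.

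Three further points were weighed:

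- Staff may not follow triage perfectly, so a few phone-positive children could be visited. That would give a sparse, selected row, which is no better basis for accuracy.
- Severe cases are called within 24 hours and all participants at 8–12 days. These calls give indirect information on disposition and care sought, but they are not the in-person reference standard that 6.10.1 specifies.
- The sentence in 6.8 about all participants may refer only to mild and moderate cases inside the zone. Even then, the cap and failed or declined deliveries are exceptions.

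**Conclusion.** The concern holds and should be fixed. For danger signs, and for any severe/non-severe contrast, sensitivity, specificity and a two-category kappa against the household exam are not estimable under this workflow. The values obtained from visited children would be fixed at 0%, 100% and 0 (sensitivity and kappa are undefined if nothing is missed). This is structural. It rests on phone-positive children going unexamined, as 6.6.3 and 6.19 say; the numerical examples rest on assumed rates and only show the scale.

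The reach is limited. Missed danger signs can be counted among visited children. Raw agreement, mild-versus-moderate congruence and the accuracy of other variables remain estimable, but only in visited children triaged non-severe by phone. The primary outcome, its sample size and the mortality suspension rule are untouched.

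**What to change.** In sections 6.10.1 and 6.18:

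1. For danger signs and severe versus non-severe, replace sensitivity, specificity and any two-category kappa with the under-triage rate: visited phone-mild/moderate children with at least one danger sign at the household, divided by all visited phone-mild/moderate children, with an exact 95% CI. State that it measures neither sensitivity nor over-triage. Bounds that treat the unexamined phone-severe cases as all true or all false positives may be added.
2. Define all other accuracy and congruence estimates, including mild versus moderate, as conditional on non-severe phone triage and a completed visit. Report how many phone-non-severe children were not visited, by reason (cap, failed or declined delivery).
3. Reconcile the statement in 6.8 that every patient participant has a paired exam with 6.6.3, 6.7 and 6.19.

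The cost is protocol and analysis wording; no new data or visits are needed. The plan would no longer promise a danger-sign sensitivity.
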